1.2.3.1 Efficacy Endpoints

Acute and late toxicity assessed by CTCAEv4 will be used to judge the tolerability of a combination of pembrolizumab and chemoradiotherapy to ensure that the treatment does not cause excess toxicity.

Flexible nasendoscopy and standard ENT examination will be performed to support the measurement the clinical response of disease. These findings will be augmented by imaging investigations performed according to the schedule of study assessment (in Section 5.0).

1.2.3.2 Biomarker Research

This protocol provides an excellent opportunity to obtain tumour tissue for translational studies. All patients will have baseline tumour biopsies available for study (in many cases these will include both fresh and formalin-fixed paraffin-embedded specimens). Patients that consent have serial blood samples drawn for analysis of circulating free tumour DNA – pre, per- and post-treatment. Patients with node-positive disease will undergo neck dissection at 12 weeks post-chemoradiotherapy.

If the patient consents, tumour biopsies will be obtained prior to commencing treatment (week 0) and, where feasible, at week 3 of treatment. We have experience of such procedures, with a high degree of successful tissue acquisition. These samples will be used for immunohistochemical analysis to identify immune infiltrates (T cells [CD4⁺, CD8⁺, CD4⁺/CD25⁺ Treg], B cells, macrophages, NK cells), levels of expression of PD1 (and other immune exhaustion markers) on immune cells, levels of PDL1 expression on tumour cells.

In addition research blood samples will be used to assess PBMC biomarkers of immune response using quantitative assays of CD4, CD8, T regulatory cell (CD4/CD25, FOXP3), B cells and NK cells will be performed. In addition, where feasible, functional assays of cytokine release will be performed.

2.0 STUDY OBJECTIVES AND ENDPOINTS

2.1 Study Objectives

2.1.1 Primary Objective

Objective: To assess the safety and tolerability of combining platin-based chemoradiotherapy (70 Gy in 35 fractions plus cisplatin (100 mg/m²) on days 1, 22 and 43) with pembrolizumab anti-PD1 monoclonal antibody in patients with HPV-ve and HPV +ve disease.

Hypothesis: It is hypothesised that pembrolizumab can be safely dosed at 200 mg every 3 weeks during cisplatin-based chemoradiotherapy in patients with locally advanced head and neck cancer.

2.1.2 Secondary Objectives

Objective: To assess progression free and overall survival.

Hypothesis: Combining pembrolizumab with chemoradiotherapy and continued use of pembrolizumab alone could lead to prolonged responses in patients.

Objective: To assess duration of clinical benefit defined as SD, PR or CR response using RECIST v1.1 by imaging and clinical examinations.

Hypothesis: High- and intermediate-risk disease have a significant chance of experiencing loco-regional or systemic failure.

2.1.3 Exploratory Objectives

Objective: To conduct exploratory translational studies of the effects of pembrolizumab on the immune responses of patients receiving radical chemoradiotherapy for high- and intermediate-risk HPV-ve and HPV+ve LA-SCCHN – these studies will include analysis of both peripheral blood mononuclear cells (PBMC) and intratumoural immune infiltrates.

Hypothesis: It is hypothesised that pembrolizumab will favourably alter the anti-tumour immune response in patients receiving cisplatin-based chemoradiotherapy for locally advanced head and neck cancer.

Objective: To study the role of measuring circulating free tumour DNA (ctDNA) as a biomarker of tumour clearance and/or recurrence.

Hypothesis: It is hypothesised that pembrolizumab will favourably alter the kinetics of ctDNA clearance in patients receiving cisplatin-based chemoradiotherapy for locally advanced head and neck cancer (in comparison with a historical control dataset that we are currently generating).

2.2 Study Endpoints

2.2.1 Primary Endpoint

1. A: To establish the maximum tolerated dose that can safely be combined with platin-based chemoradiotherapy in patients with HPV-ve and HPV+ve LA-SCCHN.
- B: To evaluate acute toxicity as measured during treatment by CTCAE v4.0.

2.2.2 Secondary Endpoints

1. To measure the PFS and overall survival at 6 months, 1 year and 2 years.
2. To measure the duration of clinical benefit using RECIST at 6 months, 1 year and 2 years.
3. To evaluate late radiotherapy toxicities as measured during treatment by LENT SOMA 52 weeks from the end of radiation therapy (week 7).

2.2.3 Exploratory Endpoints

A. Peripheral blood analysis

1. PBMC biomarkers of immune response: Quantitative assays of CD4, CD8, T regulatory cell (CD4/CD25, FOXP3), B cells and NK cells will be performed. In addition, where feasible, functional assays of cytokine release will be performed.
2. Analysis of circulating free tumour DNA – pre, per- and post-treatment.

B. Tumour Biopsy samples

1. Immunohistochemical analysis to identify immune infiltrates (T cells [CD4⁺, CD8⁺, CD4⁺/CD25⁺ Treg], B cells, macrophages, NK cells), levels of expression of PD1 (and other immune exhaustion markers) on immune cells, levels of PDL1 expression on tumour cells.

3.0 STUDY DESIGN

3.1 Overall Study Design

This will be a single centre phase 1 dose-escalation study to confirm the safety of combining pembrolizumab with standard platin-based chemoradiotherapy in patients with stage IV high- and intermediate-risk locally-advanced head and neck cancer.

advanced squamous cell carcinoma of the head and neck (LA-SCCHN). 6-36 patients (18 HPV+ve and 18 HPV-ve) will be recruited in a standard 3+3 dose-escalation trial design with an expansion cohort at the maximum tolerated dose (or 200 mg, if no DLT is defined). A pre-loading dose of 100 or 200mg (dependent on dosing level) of pembrolizumab will be given once the patient has completed the screening period. Patients will then return 2 weeks later to begin cycle 1 of a regimen of pembrolizumab 3 weekly at a dose of 100 or 200mg (dependent on dosing level) for a total of 7 cycles (3 during chemoradiotherapy and 4 after chemoradiotherapy).

Parallel studies in HPV-ve and HPV +ve disease will be conducted (note these patients may have different patterns of co-morbidity and, hence, different treatment-related toxicities). The primary endpoint of the study will be safety and tolerability. Dose-limiting acute toxicity will be assessed during administration of study drug according to CTCAEv4.0. The maximum tolerated dose of study drug (or 200 mg in the absence of DLT) will be used in a subsequent randomised phase 2 study comparing standard-of-care therapy with standard-of-care therapy plus study drug.

3.2 Treatment Regimen

All patients will receive radical platin-based chemoradiotherapy (70 Gy in 35 fractions plus cisplatin 100 mg/m² or carboplatin Area under the curve (AUC) = 5) on days 1, 22, 43 in combination with Pembrolizumab.

Pembrolizumab (at the dose level under current evaluation –100/200mg) will be administered as a pre-loading dose after the completion of the screening period, cycle 1 which will be 2 weeks after the pre-loading dose and then every 3 weeks for a total of 7 cycles (3 during chemoradiotherapy and 4 after chemoradiotherapy) or until disease progression, presence of unacceptable toxicities or withdrawal. Both the HPV-ve and HPV+ve arms will run simultaneously.

A minimum of 3 patients will be required per HPV cohort at each dose level. A minimum gap of 1 week should be left between the recruitment of the first and second patient in a new dosing level to mitigate against multiple patients suffering from any acute toxicity. If no dose limiting toxicity is observed in the first 3 patients at a dose level, pembrolizumab will be escalated to the next dosing level. If 1 in 3 patients experience a dose limiting toxicity then the cohort will be expanded to 6 patients. If 1 in 6 patients experience a DLT then the dose will be escalated to the next dosing level. However if ≥ 2 in 6 patients experience a DLT then the maximum administered dose (MAD) will have been reached and the previous dosing level, the MTD, should be used for the expansion phase. If $2/3$ patients experience a DLT the MTD will have been reached and the previous dosing level should be used for the expansion phase, if this occurs at dose level 1 the study would be stopped.

Once the MTD has been determined the trial enters the expansion cohort whereby a further 6 are treated in each HPV cohort with the determined dosage of pembrolizumab in combination with platin-based chemoradiotherapy.

[figure not shown]
3.3 Dose Levels

This study has 2 dosing levels. The rate of entry and escalation to the next dose level will depend upon assessment of the toxicity profile of patients entered at the previous level. Toxicity and assessment for DLT period will be assessed during treatment and up until 6 weeks after the completion of chemoradiotherapy. The DLTs for this study will be defined as: Grade 4 thrombocytopenia (or Grade 3 with haemorrhage); Grade 4 neutropenia lasting >7 days (or Grade 3 with fever); Grade 4 anemia; Grade 4 mucositis (or Grade 3 with confluent lesions lasting >6 weeks after the end of radiotherapy); >2 weeks toxicity-related treatment delay; or any other \geq Grade 3 non-hematologic toxicity (except nausea and vomiting) which in the opinion of the investigator is considered dose-limiting. The results of each dosing level will be reviewed by the safety review committee (SRC) before recruitment to the next dose level can begin.

Escalation to the next dose level will not proceed until the following criteria are satisfied:

- **If 0/3 patients** experience any of the above mentioned DLT's escalation to the next dose level can proceed.
- **If 1/3 patients** experiences any of the above mentioned DLT's the dose level will be expanded to a total of 6 patients.
 - If 1/6 patients experience any of the above mentioned DLT's then escalation to the next dose level can proceed.
 - If \geq 2/6 patients in a specific dose level experience any of the above mentioned DLT's the maximum tolerated dose will have been reached and all subsequent patients will be recruited at the previous dose level.
- **If 2/3 patients** experience any of the above mentioned DLT's then the maximum tolerated dose will have been reached and the expansion cohort phase will begin at the previous dose level. If the MTD is reached at dose level 1 the study will be stopped.

3.4 Study Flow Chart

3.5 Follow-up Visits

3.5.1 Post-Chemoradiotherapy Follow-up Visits

Patients will be seen weekly for 4 weeks after completion of chemoradiotherapy. After this they will then be seen 3 weekly at the administration of the next cycles of pembrolizumab.

3.5.2 Post-Treatment Follow-up (A) Visit – Patients who complete all cycles of pembrolizumab

Patients who complete all cycles of pembrolizumab without disease progression or suffering unacceptable toxicities will be seen at 4 weeks and 8 weeks after the last dose of pembrolizumab. Procedures and assessments will be performed as defined in the schedule of study assessment (Table 2).

3.5.3 Post-Treatment Follow-up (B) Visit – Patients who discontinue without progression.

Patients who discontinue pembrolizumab for any reason other than disease progression will be seen 8 weeks after the last dose of pembrolizumab. Procedures and assessments will be performed as defined in the schedule of study assessment (Table 2).

3.5.4 12 Weeks Safety Follow-up (SFU) Visit

In addition to the above follow up all patients are expected to attend a mandatory safety follow-up visit conducted at 12 weeks after the last dose of pembrolizumab or before the initiation of a new anti-cancer treatment, whichever comes first. All AEs that occur prior to the safety follow-up visit should be recorded as described in section 7.0. After the safety follow-up any unresolved AEs at the patient's last visit should be followed up for as long as medically indicated, but without further recording in the CRF.

3.5.5 Post-Safety Follow-up (A) Visits – Patients who complete all cycles of pembrolizumab.

Patients who complete all cycles of pembrolizumab without disease progression or suffering unacceptable toxicities will move into the post-safety follow-up (A) phase. These patients will be assessed every 4 weeks from SFU for 9 months or until the patient suffers disease progression, they begin a new anti-cancer treatment or they withdraw. Each follow up visit will monitor disease status and assess for any new anti-cancer therapies. If a patient progresses or begins a new anti-cancer therapy they will move to the survival follow-up phase.

3.5.6 Post-Safety Follow-up (B) Visits – Patients who discontinue without progression.

Patients who discontinue pembrolizumab for any reason other than disease progression will move into the post-safety follow-up (B) phase. These patients will be assessed every 8 weeks from SFU for 9 months or until the patient suffers disease progression, they begin a new anti-cancer treatment or they withdraw. Each follow-up visits will monitor disease status and assess for any new anti-cancer therapies initiated. If a patient progresses or begins a new anti-cancer therapy they will move to the survival follow-up phase.

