Treatment / Main Study Procedures	
Patients will be registered to receive pembrolizumab in combination with platin-based chemoradiotherapy. A pre-loading dose of 100 or 200mg (dependent on dosing level) of pembrolizumab will be given once the patient has completed the screening period. Patients will then return 2 weeks later to begin cycle 1 of a regimen of pembrolizumab 3 weekly at a dose of 100 or 200mg (dependent on dosing level) for a total of 7 cycles (3 during chemoradiotherapy and 4 after chemoradiotherapy).
 
Clinical assessments will be undertaken at the pre-loading dose and then every 3 weeks on the day on which the drug is administered. Patients will continue on this regimen until they complete all 8 doses of pembrolizumab, suffer disease progression, unacceptable toxicities, discontinue the study medication for any other reason or withdraw from the study. Chemoradiotherapy will begin with the cycle 1 dose of pembrolizumab and will continue for 35 fractions over a period of 7 weeks.
 
After the last dose of pembrolizumab patients will be expected to attend post-treatment follow-up visits as described below and/or safety follow-up (SFU) at 12 weeks or earlier if initiating a new anti-cancer treatment. Follow up requirements for patients are as follows:
 
 • If a patient completes all 8 doses of pembrolizumab without disease progression or unacceptable toxicities they will be seen at 4 weeks and 8 weeks after the last dose of pembrolizumab for the post treatment follow up. They will then return at 12 weeks for the SFU and after this be followed up every 4 weeks for 9 months to assess for disease status and the initiation of a new anti-cancer treatment. If the patient progresses or begins a new treatment during this time then they will move into the survival follow up every 12 weeks by telephone for overall survival until death, withdrawal of consent, or the end of the study • If a patient discontinues for reasons other than disease progression they will be seen at 8 weeks after the last dose of pembrolizumab for the post treatment follow up. They will then return at 12 weeks for the SFU and after this be followed up every 8 weeks for 9 months to assess disease status until progression, initiating a non-study cancer treatment or withdrawal. If a patient progresses or begins a new anticancer therapy patients will be followed every 12 weeks by telephone for overall survival until death, withdrawal of consent, or the end of the study. • If a patient progresses at any time in the study they would be expected to complete a SFU visit at 12 weeks after their last dose of pembrolizumab or before the initiation of a new anti-cancer treatment, whichever comes first. They will then move into survival follow up and will be followed every 12 weeks by telephone for overall survival until death, withdrawal of consent, or the end of the study. 
Patients will also undergo tumour assessment by RECIST 1.1 at screening, 8 weeks post chemoradiotherapy (cycle6) and then every 12 weeks for 12 months (irrespective of delays

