4.4 Patient Replacement Strategy

Additional patients may be enrolled in a given cohort to ensure that the required number of evaluable patients in each cohort is achieved. A patient that discontinues the trial for progressive disease or a drug-related AE will not be replaced. Patients receiving at least one radiotherapy fraction and one dose of pembrolizumab will also be counted in the evaluable population for the primary endpoint of treatment-related toxicity of patients for the respective cohort.

Patients found to be ineligible during screening or do not continue onto treatment or do not reach the visit 6 weeks post chemoradiotherapy can be replaced by new patients in that cohort to ensure there is a minimum of 3 (or 6 if required) patients in each cohort.

All other patients will be assessed for toxicity and secondary endpoints.

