5.3 Clinical Procedures/Assessments

5.3.1 Adverse Event (AE) Monitoring

The investigator / designee will assess each patient for potential new or worsening AEs as specified in the schedule of study assessment (Table 2) and more frequently if clinically indicated. Adverse events will be graded and recorded from the first dose of pembrolizumab until the patients 12 weeks safety follow-up visit according to NCI CTCAE Version 4.0 (see Appendix 2). Toxicities will be characterized in terms regarding seriousness, causality, toxicity grading, and action taken with regard to trial treatment.

All AEs of unknown aetiology associated with pembrolizumab exposure should be evaluated to determine if it is possibly an event of clinical interest (ECI) of a potentially immunologic aetiology (irAE). See Section 7 and Appendix 5 regarding the identification, evaluation and management of AEs of a potential immunological aetiology. Please refer to section 7 for detailed information regarding the assessment and recording of AEs.

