12.0 APPENDICES

12.1 Appendix 1: Dose-Modification Guidelines for Chemotherapy

Toxicities are to be assessed according to the CTCAE version 4.0. Patients should be monitored closely for toxicities, and the cisplatin dosing should be withheld or reduced according to degrees of toxicity.

The guiding principle for dose modifications in patients receiving therapy with MK-3475, cisplatin, and radiotherapy is to modify only the treatment responsible for the toxicity in question, if the toxicity is entirely consistent with 1 of the 3 treatments. Therapy with the other treatment may continue while treatment with the presumptive causative agent is interrupted or modified. In contrast, if the toxicity in question cannot be easily attributed to 1 of 3 treatments, then further treatment with each of the agents may need to be discontinued, interrupted, or modified. Treatment modifications will, however, take into account that radiation therapy is the foundation therapy being employed, and adjustments to the radiotherapy regimen will only be made if unavoidable due to the toxicity observed.

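### Adverse event recording can close before the DLT window in patients whose last pembrolizumab dose is the pre-loading dose or cycle 1

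*Combined protocol and SAP*

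**What the plan says.** The DLT window is anchored on chemoradiotherapy. Section 3.3: "Toxicity and assessment for DLT period will be assessed during treatment and up until 6 weeks after the completion of chemoradiotherapy". Section 12.1.4 repeats the six-week limit. One listed DLT is Grade 3 mucositis with confluent lesions, which counts only if it persists more than six weeks beyond radiotherapy.

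Recording is anchored on pembrolizumab. Section 5.3.1: "Adverse events will be graded and recorded from the first dose of pembrolizumab until the patients 12 weeks safety follow-up visit". Section 7.2 uses the same limits, and 7.5.1 does so for SAEs. Section 3.5.4 sets the SFU at 12 weeks from the last dose, or sooner if a new anti-cancer therapy begins. It then ends CRF entry while clinical follow-up goes on: "After the safety follow-up any unresolved AEs at the patient's last visit should be followed up for as long as medically indicated, but without further" (the closing words of that sentence rule out more CRF entries). For patients who stop early without progression, 3.5.3 gives one visit before the SFU: "Patients who discontinue pembrolizumab for any reason other than disease progression will be seen 8 weeks after the last dose of pembrolizumab".

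Section 4.4 decides who counts. A single radiotherapy fraction plus a single pembrolizumab dose makes a patient evaluable for treatment-related toxicity. It also says: "A patient that discontinues the trial for progressive disease or a drug-related AE will not be replaced". Patients who do not reach a visit six weeks after chemoradiotherapy may be replaced.

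Section 12.1 lets the other treatments go on when one agent is held responsible for a toxicity: "Therapy with the other treatment may continue while treatment with the presumptive causative agent is interrupted or modified".

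**The concern.** The two clocks start from different events, and no section says the later one governs. For most patients this is harmless, because pembrolizumab continues after chemoradiotherapy and the SFU falls well beyond the DLT window. It is not harmless when pembrolizumab stops very early and chemoradiotherapy goes on. The patient stays in the DLT denominator, but the CRF closes before the period in which a DLT can occur.

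The DLT count drives the 3+3 decision in cohorts that start at three patients. Under 3.3, 1/3 means expansion to six and 0/3 means escalation, so one unrecorded DLT can change the decision. The possible error runs one way: DLTs can be missed, not added. Observation is shortest in those who stopped soonest, who include patients who stopped for toxicity.

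**Working it through.** **Inputs.** Chemoradiotherapy starts with cycle 1 and "will continue for 35 fractions over a period of 7 weeks" (Trial Summary). Pembrolizumab is given as a pre-loading dose, then "cycle 1 which will be 2 weeks after the pre-loading dose and then every 3 weeks for a total of 7 cycles" (section 3.2). With cycle 1 at week 0, doses fall at weeks -2 (pre-loading), 0 (C1), 3 (C2), 6 (C3), 9, 12, 15 and 18.

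**Check against the plan's own calendar.** The Trial Summary puts the first on-study scan 8 weeks after chemoradiotherapy, at cycle 6; Table 2 puts it at week 15. Chemoradiotherapy end + 8 = 7 + 8 = 15, and C6 = 0 + 5 × 3 = 15. Both agree, so chemoradiotherapy ends at week 7.

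**DLT window end** = 7 + 6 = week 13.

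**Follow-up (B) visit** = last dose + 8. **SFU** = last dose + 12. **Gap** = 13 − SFU week; a positive gap means recording closes first.

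| Last dose | Week | (B) visit | SFU, recording closes | Gap (weeks) |
|---|---|---|---|---|
| Pre-loading | -2 | 6 | 10 | +3 |
| C1 | 0 | 8 | 12 | +1 |
| C2 | 3 | 11 | 15 | −2 |
| C3 | 6 | 14 | 18 | −5 |

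**Sensitivity.**
- Each week of chemoradiotherapy overrun adds one week to every gap. C2 becomes positive only beyond a 2-week overrun (15 − 13), and C3 only beyond 5 weeks (18 − 13).
- New anti-cancer treatment can bring the SFU forward after any last dose.
- Section 6.3.7 allows dosing 3 days either side of the schedule. If only the C1 dose moves, its gap is 1 ± 3/7, or 0.6 to 1.4 weeks.

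**Does a later visit fill the gap?** Section 3.5.6 continues every 8 weeks from the SFU, so the next visit is at week 18 (10 + 8) or week 20 (12 + 8). Its stated purpose is disease status and new therapy. Table 2 has visits at weeks 12 and 15 but none at week 13, so the six-week visit that 4.4 relies on is not scheduled for anyone. Table 2's follow-up columns are misaligned in the text available to me, and I have not relied on their AE row.

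**The mucositis DLT.** It cannot be confirmed before week 13. With the SFU at week 10 or 12, mucositis still present would be in the CRF with its grade and onset, but the duration that makes it a DLT would not.

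**Illustration of the effect on escalation.** The rates here are assumed, not taken from the documents. With true DLT probability p, the chance of escalating is (1 − p)³ + 3p(1 − p)² × (1 − p)³. At p = 0.30 this is 0.343 + 0.151 = 49.4%. If 5%, 10% or 20% of all DLTs went unrecorded, p becomes 0.285, 0.27 or 0.24 and the chance rises to 52.5%, 55.7% or 62.2%. At p = 0.20 it goes from 70.9% to 73.0%, 75.2% or 79.3%. The gap affects few patients, so the upper end is unlikely.

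**The case against.** The case for leaving the text alone has several parts.

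- **DLT assessment is its own instruction.** Sections 3.3 and 12.1.4 require it to week 13 whether or not pembrolizumab continues, so a careful site would do it. This stands, but 3.5.4 and 5.3.1 close the record earlier, and that conflict is the point.
- **Other contacts exist.** Section 3.5.1 sets weekly visits for four weeks after chemoradiotherapy (weeks 8 to 11) without restricting them to patients still on drug. Section 5.3.9.1 requires examination, including nasendoscopy, every 3 weeks to 8 weeks after chemoradiotherapy (week 15). Persistent mucositis would be seen there. This is real cover. However, 3.5.1 goes on to assume further pembrolizumab cycles, its weekly visits end before week 13, and 5.3.9.1 is aimed at disease resolution, not AE recording.
- **Serious events are caught.** Section 7.2 records SAEs throughout the study, and 7.5.1 requires related SAEs outside the period to be reported. This stands for serious events. It leaves non-serious DLTs.
- **Related AEs are followed on.** Section 7.2 continues follow-up of events judged related, but does not clearly extend CRF recording past the SFU and does not reach new events.
- **Many of these patients may already have a counted DLT.** Table 10 mostly ties permanent discontinuation to Grade 3–4 or unresolved events. DLTs are counted per patient, so a second event changes nothing. This limits the effect: what matters is a first DLT that is established only in the gap.
- **Replacement is allowed.** Section 4.4 permits it for patients who miss the six-week visit, but does not require it, and Table 2 does not schedule that visit.
- **Appendix 1 speaks of interruption or modification, not discontinuation.** True, but Table 10 discontinues pembrolizumab alone, and Appendix 1 treats radiotherapy as the foundation therapy, so continuing chemoradiotherapy after a permanent stop is a reasonable reading.

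**Conclusion.** The concern holds for a small group. If the last dose is pre-loading or C1 and chemoradiotherapy continues on schedule, CRF recording closes 3 weeks or 1 week before the DLT window ends. The shortfall grows if chemoradiotherapy overruns or new anti-cancer treatment brings the SFU forward. A first non-serious DLT in that gap, or the duration defining the mucositis DLT, may go unrecorded. This is a risk, not a demonstrated loss; the documents give no frequency, and few patients are likely to be affected. It should be fixed because the count is the primary endpoint's decision variable in cohorts of three.

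Two stronger readings are tempting and are not supported. A reader might infer that everyone who stops pembrolizumab during chemoradiotherapy is affected. After C2 or C3, recording runs to week 15 or 18, past week 13, unless chemoradiotherapy overruns by more than 2 or 5 weeks or the SFU is brought forward. A reader might also infer that worst-grade acute toxicity (primary endpoint B) is biased downwards. That endpoint is measured during treatment. In these patients treatment ends at week 7, and recording runs to week 10 even in the shortest case when the SFU is not brought forward.

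The conclusion assumes a 7-week course starting with C1, and that the recording rules in 3.5.4 and 5.3.1 are applied as written.

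**What to change.** - In 3.5.4, 5.3.1, 7.2 and 7.5.1, run AE and SAE recording to the later of the SFU and six weeks after the end of chemoradiotherapy. For on-schedule patients this moves closure from week 10 or 12 to week 13 and leaves C2 and C3 stoppers unchanged.
- In 3.5.1 and 3.5.3, state that the post-chemoradiotherapy visits also apply to patients who have stopped pembrolizumab.
- In Table 2, schedule the six-week post-chemoradiotherapy visit that 4.4 already refers to, and name it as the DLT assessment.

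The cost is amendment wording, a few extra CRF entries in early stoppers, and one scheduled assessment. No dose or rule for stopping treatment changes.
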